## 2. Objectives

### 2.1. Primary Objectives

- To evaluate the efficacy of oral ibrexafungerp versus placebo in preventing recurrences of vulvovaginal candidiasis (VVC) in subjects with recurrent VVC (RVVC) based on Clinical Success.

### 2.2. Key Secondary Objective:

- To evaluate the efficacy of oral ibrexafungerp versus placebo in preventing recurrences of VVC in subjects with RVVC based on Mycologically Proven Recurrences at Test of Cure (TOC).

### 2.3. Other Secondary Objectives:

- To evaluate the efficacy of oral ibrexafungerp versus placebo in preventing recurrences (Mycologically Proven, Presumed or Suspected) of VVC in subjects with RVVC.
- To evaluate the efficacy of oral ibrexafungerp versus placebo in preventing recurrences of VVC in subjects with RVVC based on the number of Recurrences (Mycologically Proven, Presumed or Suspected) of VVC.
- To evaluate the efficacy of oral ibrexafungerp versus placebo in subjects with RVVC based on Quality of Life (QOL) outcomes.
- To evaluate the safety and tolerability of oral ibrexafungerp in subjects with RVVC.

## 3. Investigational Plan

### 3.1. Overall Study Design and Plan

This study is a Phase 3, multicenter, randomized, double-blind, placebo-controlled study to evaluate the efficacy and safety of oral ibrexafungerp (formerly “SCY-078”) compared to placebo in female subjects 12 years and older with RVVC. The primary objective of the study is to evaluate the efficacy of oral ibrexafungerp versus placebo in preventing recurrences of VVC in subjects with RVVC based on Clinical Success.

The study will consist of a Screening visit, an Acute Phase with open-label fluconazole and a Prevention of Recurrence Phase with randomized ibrexafungerp or placebo. Screening and the beginning of the Acute Phase (Day -14) may occur on the same day. Approximately 320 subjects are planned to be enrolled into the open-label Acute Phase of the study in order to randomize approximately 240 subjects into the double-blind Prevention of Recurrence Phase, which will consist of 6 monthly, single-day treatments with the randomized study drug.

A Nested Sub-Study will be made available to subjects who fail treatment with fluconazole during the Acute Phase and are not eligible for randomization into the Prevention of Recurrence Phase.

The schedule of study assessments is presented in [Appendix 1](#).

## 3.2. Study Endpoints

### 3.2.1. Primary Endpoints

- Efficacy as measured by the percentage of subjects with documented Clinical Success (defined as subjects having a TOC evaluation and no Mycologically Proven, Presumed or Suspected Recurrences of VVC) up to Week 24 (TOC).

### 3.2.2. Key Secondary Endpoint:

- Efficacy as measured by the percentage of subjects with no Mycologically Proven Recurrence (defined as an episode of VVC with a total composite score  $\geq 3$  on the Vulvovaginal Signs and Symptoms [VSS] Scale and a culture positive for *Candida* spp. that required antifungal treatment) up to Week 24 (TOC).

### 3.2.3. Other Secondary Endpoints:

Efficacy as measured by:

- The percentage of subjects with no Mycologically Proven Recurrence up to Week 4, Week 8, Week 12, and Week 36 (end of follow-up [EOFU]);
- The time to the first Recurrence (Mycologically Proven, Presumed or Suspected) of VVC through EOFU;
- The percentage of subjects with Mycological Eradication (negative fungal culture) at Week 12, Week 24 (TOC) and Week 36 (EOFU);
- The percentage of subjects with no Mycologically Proven, Presumed or Suspected Recurrences up to Week 4, Week 8, Week 12 and Week 36 (EOFU);
- The percentage of subjects with no Mycologically Proven or Presumed Recurrences up to Week 4, Week 8, Week 12, Week 24 (TOC) and Week 36 (EOFU);
- The proportion of subjects in four ordered categories related to the number of Recurrences (Mycologically Proven, Presumed or Suspected) of VVC from Baseline (Day 1) to Week 24 (TOC) and Week 36 (EOFU). The three categories of recurrence are defined as (i) 0 episode, (ii) 1 episode, (iii) 2 to 3 episodes, and (iv)  $\geq 4$  episodes;
- The absolute number of Mycologically Proven, Presumed or Suspected Recurrences from Baseline (Day 1) to Week 24 (TOC) and Week 36 (EOFU);
- Absolute improvement in QOL outcomes at Week 12, Week 24 (TOC) and Week 36 (EOFU) as measured by EQ-5D, SF-36 and FSDDS;

Safety and tolerability as measured by:

- Adverse events (AEs), vital signs, treatment discontinuation and safety laboratory tests.

### 3.3. Treatments

#### Acute Phase

Subjects who meet all study eligibility criteria at screening will enter the Acute Phase of the study and will receive oral fluconazole, as follows:

- Oral fluconazole 150 mg QD on Days -14, -11 and -8

The first dose of fluconazole will be administered on Day -14 at the study site, after all other visit procedures have been done. Subjects will self-administer the remaining doses at home.

#### Prevention of Recurrence Phase

Subjects who have a culture-confirmed *Candida spp.* infection from the sample collected at screening, achieve significant resolution of their vulvovaginal signs and symptoms on fluconazole (defined as a total composite score  $\leq 2$  on the VSS Scale) at Baseline (Day 1) and continue to meet all other eligibility criteria will be entered into the Prevention of Recurrence Phase and randomized at a 1:1 ratio to one of the following two treatment groups:

- Oral ibrexafungerp administered as a single-day treatment repeated every 4 weeks (28 days [ $\pm 3$ ]) for a total of 6 single-day treatments (Baseline [Day 1], Week 4, Week 8, Week 12, Week 16 and Week 20). Each single-day treatment will consist of two doses of 300 mg each given 12 ( $\pm 4$ ) hours apart (total single-day dose = 600 mg);
- Matching oral placebo administered as a single-day treatment repeated every 4 weeks (28 days [ $\pm 3$ ]) for a total of 6 single-day treatments (Baseline [Day 1], Week 4, Week 8, Week 12, Week 16 and Week 20). Each single-day treatment will consist of two doses of placebo given 12 ( $\pm 4$ ) hours apart.

Subjects will receive their first dose of double-blind study drug at the site and will self-administer the remaining doses at home. Subjects must take the two doses of study drug 12 hours apart ( $\pm 4$  hours), preferably with or immediately after a meal. Subjects will record study drug dosing details in their study diary.

A Nested Sub-Study will be made available to subjects who fail treatment with fluconazole during the Acute Phase and are not eligible for randomization into the Prevention of Recurrence Phase. All eligible subjects will receive oral ibrexafungerp administered as a single-day treatment consisting of two 300-mg doses (total dose = 600 mg) given 12 hours apart ( $\pm 4$  hours) at Baseline (Day 1). A detailed analysis plan for the Nested Sub-study will be provided in the [Appendix 4](#).

#### 4. General Statistical Considerations

Continuous data will be described using descriptive statistics (i.e. n, mean, standard deviation (SD), median, minimum, and maximum). Categorical data will be described using the subject count and percentage in each category. For the summary statistics of all numerical variables unless otherwise specified, minimum and maximum will be displayed to the same level of precision as reported. Mean and median will be displayed to one level of precision greater than the data collected. Standard deviation / standard error will be displayed to two levels of precision greater than the data collected. P-values will be rounded to three decimal places. If a p-value is less than 0.001 it will be reported as “<0.001.” If a p-value is greater than 0.999 it will be reported as “>0.999.” Data will be displayed in all listings sorted by treatment group.

Subjects will be identified in the listings by the subject identification number concatenated with the investigator number.

When count data are presented, the percentage will be suppressed when the count is zero in order to draw attention to the non-zero counts. A row denoted “Missing” will be included in count tabulations where specified on the shells to account for dropouts and missing values. The denominator for all percentages will be the number of subjects in that treatment within the analysis set of interest, unless otherwise specified.

Unless otherwise specified, baseline will be defined as the last non-missing assessment prior to or on the date (and time if appropriate) of the first dose of study drug. Change from baseline is defined as post-baseline value – baseline value.

The study day will be calculated as follows:

If the assessment date occurs on or after the date of the first dose of study drug:

$$\text{Study day} = \text{assessment date} - \text{first dose date} + 1.$$

If the date of interest occurs before the date of the first dose of study drug:

$$\text{Study day} = \text{assessment date} - \text{first dose date}$$

There is no study day 0.

All analyses will be conducted using SAS Version 9.3 or higher. All statistical tests will be two-sided and interpreted at a 5% significance level.

This statistical analysis plan is created for the main study. Regarding the detailed description of the statistical analysis of the nested sub-study, please refer to the [Appendix 4](#).

##### 4.1. Sample Size

The primary endpoint of the study is the percentage of subjects with documented Clinical Success up to Week 24 (TOC). Assuming response rates of 65% and 43% for ibrexafungerp and placebo, respectively; 90% power; and an alpha level of 0.05, approximately 240 subjects randomized at a

1:1 ratio are needed to declare a difference between ibrexafungerp and placebo at Week 24 based on Fisher's Exact test.

In order to be randomized, a subject should have achieved the proposed significant resolution of signs and symptoms (total composite score  $\leq 2$  on the VSS Scale) after receiving fluconazole therapy for an acute episode and have a positive culture for *Candida* spp. from the sample collected at screening. It is estimated that approximately 320 subjects will need to enter the Acute Phase to provide 240 subjects randomized to the Prevention of Recurrence Phase. Enrollment into the Acute Phase will be discontinued when approximately 240 subjects have been randomized.

#### **4.2. Randomization, Stratification and Blinding**

Approximately 320 subjects are planned to be enrolled into the open-label Acute Phase of the study in order to randomize approximately 240 subjects at a 1:1 ratio to one of the two study treatment groups.

An interactive web-based response system (IWRS) will be used to administer the randomization schedule. Biostatistics will generate the randomization schedule using SAS® software Version 9.3 or later (SAS Institute Inc, Cary, North Carolina) for IWRS, which will link sequential subject randomization numbers to treatment codes.

Neither the subjects nor the investigators will be aware of the treatment assignment for the subjects. The study drugs will be identical in number and appearance. Blinding will be maintained throughout the study by use of active or placebo dosage forms of similar appearance.

A subject's treatment assignment will not be broken until the end of the study unless medical treatment of the subject depends on knowing the study treatment the subject received. In the event that the blind needs to be broken because of a medical emergency, the investigator may unblind an individual subject's treatment allocation. As soon as possible, the investigator should first contact the medical monitor to discuss the medical emergency and the reason for revealing the actual treatment received by that subject. No investigator is in full rights to unblind a subject on medical reasons without prior consultation with the sponsor or medical monitor.

Eligible subjects will be stratified at randomization based on the presence or absence of uncontrolled diabetes mellitus, defined as A1C levels  $\geq 8.00\%$  at Baseline (Uncontrolled diabetes mellitus: YES or NO), and by geographical region (USA or Ex-USA).

#### **4.3. Analysis Set**

Intent-to-Treat (ITT) Set: All randomized subjects who received at least one dose of study drug (ibrexafungerp or placebo).

Modified Intent-to-Treat (mITT) Set: All randomized subjects who received at least one dose of study drug (ibrexafungerp or placebo), who have a confirmed mycological culture for yeast at Screening and a negative culture for yeast at Baseline (Day 1).

Per-Protocol (PP) Set: All mITT subjects who did not have major protocol deviations likely to affect study efficacy and who have available data at the TOC visit. Note that subjects who discontinue due to a study-drug-related AE will be classified as failures for the analyses of efficacy under the PP population.

Safety Set (SS): All randomized subjects who received at least one dose of study drug (ibrexafungerp or placebo) and who have at least one post-baseline evaluation.

#### **4.4. Handing of missing data**

##### **4.4.1. Non-Responder Imputation (NRI) for Categorical Responses**

For clinical responses which described in section 8.1, and 8.2.1, a subject who has not previously experienced a failure response of the endpoint of interest and does not have the required assessment of potential recurrence data at Week 4 (or Week 8, Week 12, Week 24 (TOC) and Week 36 (EOFU)) for any reason will be considered as failure in the analysis of the specified time point. If one or more of the required assessments of potential recurrence are not completed within Week 4 (or Week 8, Week 12, Week 24 (TOC) and Week 36 (EOFU)), the subject will be considered as failure. Randomized and took at least 1 study treatment patients without at least 1 post-baseline observation will also be defined as failure for the NRI analysis.

For mycological outcome, subjects will be considered a non-responder for the NRI analysis if their mycological outcome cannot be determined due to early termination before the specified visit or missing mycological data at the specific visit. Randomized subjects without at least 1 post-baseline observation will also be defined as non-responder for the NRI analysis.

Randomized subjects without study treatment will be excluded from all analysis.

The NRI may be applied at any time point specified for analysis.

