9.0 Study Endpoints

9.1 Primary Endpoint

- Efficacy as measured by the percentage of subjects with documented Clinical Success (defined as subjects having a TOC evaluation and no Mycologically Proven, Presumed or Suspected Recurrence of VVC) up to TOC (Week 24).

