18.4 Handling of Missing Data, Dose Adjustments, and Early Withdrawals

For the efficacy analyses, subjects who do not have a TOC (Week 24) assessment will be assigned as treatment failures. For subjects who withdraw from the study early, every effort will be made to collect TOC or EOFU visit information (as applicable) at the point of withdrawal. Missing data will be further described in the SAP for early withdrawal subjects.

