18.6.2 Efficacy Analyses

The efficacy analyses will be conducted using the ITT (primary analysis population), mITT, and PP populations. The efficacy parameters will be evaluated comparing the ibrexafungerp treatment group versus the placebo group.

The primary endpoint, the percentage of subjects with documented Clinical Success up to TOC (Week 24), will be analyzed using a Cochran-Mantel-Haenszel (CMH) test adjusted for site; p-values and 95% confidence intervals will be presented. Subjects whose results are missing at TOC (Week 24) will be imputed as failures in the analysis. In the event that model convergence is an issue with a stratified analysis, alternative

methods for accounting for site, or an unstratified analysis will be considered. A sensitivity analysis will be performed on the ITT population where subjects with missing values will be removed from the analysis.

For other continuous efficacy endpoints, a two-way analysis of variance (ANOVA) model will be used including effects for treatment and site; p-values and 95% confidence intervals will be presented. For other categorical endpoints, the CMH test adjusted for site will be performed, and p-values and 95% confidence intervals will be presented.

For the ordered categorical endpoint, a proportional odds model will be fitted accounting for the effects of treatment and site. The proportional odds model will fit an ordered regression model for the ordinal dependent variable as described by McCullagh (1980). If the assumption of proportional odds is violated alternative analyses will be considered which require a weaker assumption.

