### 8.1. Primary Endpoint

The primary efficacy endpoint is defined as the proportion of ITT subjects who have documented Clinical Success (defined as subjects having a TOC evaluation and no Mycologically Proven, Presumed or Suspected Recurrences of VVC) up to Week 24 (TOC).

Clinical success will be assessed according to the following definitions:

- Clinical success: Subjects having a TOC evaluation and no Mycologically Proven, Presumed or Suspected Recurrences of VVC prior to or at the TOC visit.
- Clinical failure: Mycologically Proven, Presumed or Suspected Recurrences of VVC prior to or at the TOC visit. For the subject who early terminated before TOC visit, the subject is considered a clinical failure.

Recurrence of VVC: In this study, Recurrence of VVC will be broken into three categories:

- Mycologically Proven Recurrence: An episode of VVC with a total composite score  $\geq 3$  on the VSS Scale and a culture positive for *Candida* spp. that required antifungal treatment.
- Presumed Recurrence: An episode of VVC with a total composite score  $\geq 3$  on the VSS Scale that required antifungal treatment and for which there is a positive KOH microscopy but no positive fungal culture.
- Suspected Recurrence: An episode of VVC that required treatment with an antifungal agent (including self-administration with over-the-counter antifungals) regardless of VSS composite score but for which there is no mycological evidence of disease, such as a positive KOH microscopy or fungal culture. It also includes an episode of VVC that requires antifungal treatment and have a total VSS composite score lower than 3 regardless of mycological results.

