#### 8.1.1. Primary Analysis

The primary efficacy analysis will be performed on the ITT set at the TOC visit and will compare the proportion of subjects, in the treatment and placebo groups, who have documented Clinical Success up to Week 24 (TOC).

The number and percentage of subjects with documented clinical success up to the TOC visit will be presented by treatment group. Meanwhile, the number and percentage of subjects with clinical

failure will be presented by the recurrence categories. A Cochran Mantel Haenszel (CMH) test adjusted for Country and uncontrolled diabetes mellitus (Yes or No) at baseline will be performed to assess the statistical significance of a difference between treatment groups in the primary efficacy analysis. Mathematically stated:

$H_0$ : Clinical Success Rate up to Week 24 (TOC) Oral ibrexafungerp 300-mg dose = Clinical Success Rate up to Week 24 (TOC) Placebo

$H_1$ : Clinical Success Rate up to Week 24 (TOC) Oral ibrexafungerp 300-mg dose  $\neq$  Clinical Success Rate up to Week 24 (TOC) Placebo

The p-value, relative risk and 95% confidence interval (CI) will be presented in the ibrexafungerp 300-mg treatment arm compared to the placebo arm. Subjects who have one or more of the required assessments of potential recurrence not completed prior to or at Week 24 (TOC) visit or subjects who withdraw from the study early will be imputed using the imputation rules described in [Section 4.4.1](#).

A sensitivity analysis using the ITT set will be performed where subjects with the imputed clinical outcome will be removed from the analysis.

Subgroup analyses will be performed in the ITT set depending on BMI category ( $\leq 35$  kg/m^2 or  $>35$  kg/m^2), geographic region (USA and EX-USA), Race (White, Black or African American, Asian, American Indian or Alaska Native, Native Hawaiian or Other Pacific Islander, and Other), Uncontrolled diabetes mellitus (Yes or No), Ethnicity (Hispanic or Latino, Not Hispanic or Latino), Number of recurrent VVC episodes in the prior year ( $<4$  times,  $\geq 4$  times) and Candida species at screening (by Genus species), severity of VVC at screening (2 categorizations of the composite score of the vulvovaginal signs and symptoms at screening will be used to evaluate the severity of VVC at screening:  $<7$ ,  $\geq 7$  and '4 - 7', '8 - 12', and ' $\geq 13$ ').

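### SAP 4.4.1 and the ITT text of 8.1.1 fail a subject for one missed interim recurrence check, although SAP 8.1 and the protocol count her as a Clinical Success; the change is undeclared and no planned ITT analysis applies the 8.1 definition

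*SAP*

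**What the plan says.** **Definition of the endpoint.** SAP 8.1: "Clinical success: Subjects having a TOC evaluation and no Mycologically Proven, Presumed or Suspected Recurrences of VVC prior to or at the TOC visit". Failure there is a recurrence up to TOC, or early termination before TOC. Protocol 9.1 has the same two conditions: "Efficacy as measured by the percentage of subjects with documented Clinical Success (defined as subjects having a TOC evaluation and no Mycologically Proven, Presumed", continuing with the suspected category.

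**Protocol rule for missing data.** Protocol 18.4: "For the efficacy analyses, subjects who do not have a TOC (Week 24) assessment will be assigned as treatment failures". Protocol 18.6.2: "Subjects whose results are missing at TOC (Week 24) will be imputed as failures in the analysis". Section 18.4 then hands on further detail in limited terms: "Missing data will be further described in the SAP for early withdrawal subjects".

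**SAP rule for missing data.** The rule in SAP 4.4.1 opens "If one or more of the required assessments of potential recurrence are not completed within Week 4 (or Week 8, Week 12, Week 24" and ends by making the subject a failure. The ITT paragraph of SAP 8.1.1 sends two groups to that rule. One is early withdrawals; the other is "Subjects who have one or more of the required assessments of potential recurrence not completed prior to or at Week 24 (TOC) visit". The mITT/PP paragraph of 8.1.1 also cites 4.4.1, but names only results missing at Week 24 and early withdrawal.

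**Sensitivity analysis.** SAP 8.1.1: "A sensitivity analysis using the ITT set will be performed where subjects with the imputed clinical outcome will be removed from the analysis".

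**Declared changes.** SAP Section 11 has seven bullets: MMRM/ANCOVA for continuous endpoints, the diabetes factor, Country for site, the safety time point, the ITT set, the mITT set, and four recurrence categories. None concerns missed recurrence assessments.

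**The concern.** The two SAP texts give different values of the primary endpoint for the same subject, so two programmers could each follow the SAP and derive different primary results. Attending TOC without a recurrence is the stated definition of success. Completing every interim check is a third condition that appears only in the imputation text.

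Three things make this harder to resolve later. The protocol leaves missing-data detail to the SAP for early withdrawals, and a subject who reaches TOC is not one. Section 11 gives no sign that a change was made. The terms *required* and *completed* are undefined: the Appendix 1 row for potential-recurrence assessment includes the Week 16 and Week 20 phone contacts and is the likely list, but neither 4.4.1 nor 8.1.1 cites it.

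At stake are who counts as a primary success, some power, and the chance that the choice between the two derivations is made or disputed after unblinding.

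**Working it through.** **1. One subject, each text.** She misses one interim check, attends TOC and has no recurrence.

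| Text | Score |
|---|---|
| Protocol 9.1, 18.4, 18.6.2 | Success: TOC result present, no recurrence |
| SAP 8.1 | Success: same two conditions, no early termination |
| SAP 4.4.1 and 8.1.1 (ITT) | Failure: one required assessment not completed |
| SAP 8.1.1 (mITT/PP) | Unclear: the stated trigger is not met, but 4.4.1 is cited |
| SAP 8.1.1 ITT sensitivity analysis | Removed |

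The conflict does not need the phone contacts to be required. A missed Week 4, 8 or 12 visit produces it too.

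**2. The plan's own figure.** Inputs from Protocol 18.0 and 18.1 and SAP 4.1: 65% v 43%, two-sided alpha 0.05, 1:1, about 240 randomized, Fisher's exact test. Exact enumeration at 120 per arm gives 90.9% power, so the stated 90% reproduces. The planned primary test is CMH. Enumerated as a single stratum (hypergeometric variance, no continuity correction, country and diabetes strata ignored), it gives 92.7%.

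**3. Effect of the strict rule.** Assumptions, none from the documents: each required pre-TOC check is missed independently with probability q, equal in both arms, and 65%/43% describe the endpoint as SAP 8.1 defines it. With m required checks, each success rate is multiplied by k = (1 − q)^m. Take m = 3 for the on-site visits (Weeks 4, 8, 12) and m = 5 if the Week 16 and 20 phone contacts also count.

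| m | q | k | Rates | Difference (points) | CMH power | Fisher power |
|---|---|---|---|---|---|---|
| – | 0 | 1 | 65.0% v 43.0% | 22.0 | 92.7% | 90.9% |
| 3 | 1% | 0.970 | 63.1% v 41.7% | 21.4 | 91.0% | 88.8% |
| 3 | 2% | 0.941 | 61.2% v 40.5% | 20.7 | 89.1% | 86.5% |
| 3 | 3% | 0.913 | 59.3% v 39.2% | 20.1 | 87.1% | 84.2% |
| 5 | 1% | 0.951 | 61.8% v 40.9% | 20.9 | 89.8% | 87.3% |
| 5 | 2% | 0.904 | 58.8% v 38.9% | 19.9 | 86.5% | 83.5% |
| 5 | 3% | 0.859 | 55.8% v 36.9% | 18.9 | 83.0% | 79.8% |

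The relative risk is 0.65k / 0.43k = 1.51 in every row. Subjects rescored at q = 3%, m = 5: 120 × 0.65 × 0.141 = 11.0 and 120 × 0.43 × 0.141 = 7.3, about 18 of 129.6 expected successes.

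**4. Unequal misses (illustration, m = 5).** With 5% missed per check on ibrexafungerp and 2% on placebo: 0.65 × 0.95^5 = 50.3% v 0.43 × 0.98^5 = 38.9%, relative risk 1.29. Reversed: 0.65 × 0.98^5 = 58.8% v 0.43 × 0.95^5 = 33.3%, relative risk 1.77.

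**5. What the sensitivity analysis removes.** It drops everyone whose outcome was imputed. That covers subjects with a missed interim check and a TOC evaluation, who are successes under 8.1, and recurrence-free early withdrawals, who are failures under 8.1. The first group is never put back as successes, so neither planned ITT analysis applies the 8.1 definition.

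**The case against.** The strict rule may be deliberate. The endpoint is documented success up to TOC, Protocol 7.2.3 speaks of rigour in assigning failures despite missing data, and the time-to-recurrence analysis in SAP 8.2.1 censors before the first missed required assessment. On this view 8.1 defines the outcome and 4.4.1 says what to do when recurrence-free status has not been fully documented. Protocol 18.0 also gives the SAP general authority to describe the analyses in detail. Intent is therefore plausible. It does not settle the matter, because both documents say what documented success means, and that definition contains no interim-check condition. The protocol's imputation rules look only at TOC.

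The effect on the planned result is also limited. SAP 8.1.1 reports a p-value, relative risk and interval, not a risk difference, and equal misses leave the relative risk alone. Unequal misses need a reason in a double-blind trial, and the documents suggest none. With three checks and 1–2% missed, power stays close to 90%. All of this stands.

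A reader might infer that the sensitivity analysis removes only would-be successes, so that its relative risk drifts upward even under equal misses. The documents do not support that. It also removes recurrence-free early withdrawals. And only the first sentence of 4.4.1 is limited to subjects without a prior failure; the sentence on missed assessments has no such limit, so who is removed depends on a reading that the SAP does not settle.

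**Conclusion.** The contradiction is in the text and needs no assumed miss rate: SAP 4.4.1 and the ITT text of 8.1.1 turn subjects who meet the stated primary definition into failures, without declaration, under undefined terms, and with no planned ITT analysis that scores them as 8.1 does.

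The size is conditional. At 1–3% missed per check, CMH power falls from 92.7% to between 91.0% and 87.1% (three checks) or between 89.8% and 83.0% (five checks). This rests on 120 per arm, equal independent misses, a single stratum, and 65%/43% not already counting missing subjects as failures. The documents do not say whether they do; if so, part of the loss is counted twice.

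Two stronger conclusions are tempting. One is that the trial is underpowered, but the documents give no miss rate and no list of required checks. The other is that the primary estimate is biased in a known direction, but equal misses leave the relative risk unchanged and unequal ones can move it either way. The point should be fixed before unblinding.

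**What to change.** In SAP 4.4.1 and 8.1.1, score the primary endpoint for ITT, mITT and PP as SAP 8.1 and the protocol define it: failure is a recurrence up to TOC, early termination before TOC, or no TOC evaluation. Use the same trigger wording in the ITT and mITT/PP paragraphs.

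Keep the any-missed-assessment rule as a labelled sensitivity analysis. Tie its required assessments to the Appendix 1 row for potential recurrence, state whether the Week 16 and 20 phone contacts count, and define what makes an assessment completed.

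If the sponsor prefers the strict rule as primary, SAP 8.1 must be amended to match, the change declared in Section 11, and TOC-only scoring added as an ITT sensitivity analysis. The same definitions of *required* and *completed* are then needed.

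The cost is SAP wording and one programming change before unblinding, with no new data. The downside of TOC-only scoring is that a treated episode between contacts that is never reported could count as a success; the retained sensitivity analysis addresses that.
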